| Table 3: Demographic and Baseline Characteristics..... | 20 |
| Table 4: ALS History Parameters..... | 21 |
| Table 5: The analysis visit windows..... | 32 |
| Table 6: Cycle definition..... | 33 |

LIST OF FIGURES

| | |
|-----------------------------|----|
| Figure 1: Study Schema..... | 10 |
|-----------------------------|----|

ABBREVIATIONS

| Abbreviations | Definitions |
|---------------|--|
| ADR | adverse drug reaction |
| AE | adverse event |
| ALT | alanine transaminase |
| ALP | alkaline phosphatase |
| ALS | amyotrophic lateral sclerosis |
| AST | aspartate transaminase |
| ATC | anatomical therapeutic chemical |
| BLQ | below limit of quantification |
| BMI | body mass index |
| CI | confidence interval |
| CRF | case report form |
| C-SSRS | Columbia suicide severity rating scale |
| CV | coefficient of variation |
| DP | decimal places |
| ECG | electrocardiogram |
| LLOQ | lower limit of quantitation |
| MedDRA | medical dictionary for regulatory activities |
| MMRM | mixed model repeated measures |
| PK | pharmacokinetics |
| PT | preferred term |
| SAP | statistical analysis plan |
| SAE | serious adverse event |
| SAF | safety population |
| SD | standard deviation |
| SOC | system organ class |
| TEAE | treatment emergent adverse event |
| TESAE | treatment emergent serious adverse events |
| ULN | upper limit of normal range |
| WHO | World Health Organization |

1. PREFACE

Amyotrophic lateral sclerosis (ALS) is a rare disease that causes progressive and fatal neurodegenerative disorders^{1,2}. Currently incurable, respiratory failure leads to death in a mean time of 2 to 4 years for the majority of ALS subjects, after the onset of the first symptoms. However, 5–10% of subjects may survive for a decade or more³.

Early stages of the disease appear in several forms and the lack of biological markers make ALS particularly difficult to diagnose. ALS is typically diagnosed by excluding other possible diseases. The El Escorial criteria have been developed and revised by the World Federation of Neurology;^{5,6} the criteria are based on clinical signs, electrophysiological and neuroimaging evidence, and allow for the diagnosis of ALS in 5 categories: definite ALS, probable ALS, probable laboratory-supported ALS, possible ALS, or suspected ALS.

ALS is a disease of unknown cause in which primary motor neurons (upper motor neurons) and secondary motor neurons (lower motor neurons) degenerate and are lost selectively and progressively. The symptoms are dominated by muscle atrophy and muscle weakness, with upper limb dysfunction, gait disturbance, dysarthria, dysphagia, and respiratory impairment appearing with the progression of illness, and with no sensory dysfunction or dysuria. As the mechanism of motor neuron death, excitatory amino acid hypothesis, free radical hypothesis, and viral infection hypothesis have been proposed.

2. INTRODUCTION

This statistical analysis plan (SAP) is based on the final global protocol amendment (v3.0) dated 27-July-2021 and country specific (v3.2) for Japan dates 22-September-2022. The plan covers statistical analysis, tabulations and listings of the study data to investigate the long-term safety and tolerability of oral edaravone in subjects with ALS over 96 weeks.

The structure and content of this SAP provides sufficient details to meet the requirements identified by the FDA and International Conference on Harmonization of Technical Requirements for Registration of Pharmaceuticals for Human Use (ICH): E9 Guidance on Statistical Principles in Clinical Trials. All work planned and reported for this SAP will follow internationally accepted guidelines, published by the American Statistical Association, and the Royal Statistical Society, for statistical practice.

The following documents were reviewed in preparation of this SAP:

- Clinical Study Protocol MT-1186-A03 Version 3.0 issued on, 27-July-2021
- Case report form (CRF) for MT-1186-A03
- ICH E9 Guidance on Statistical Principles for Clinical Trials.

- ICH E3 Structure and Content of Clinical Study Reports (CSRs)
- ICH E14 (may, 2005) clinical evaluation of QT/QTC interval prolongation

Any statistical analysis details described in this document supersede the description of statistical analysis in the protocol. In case of major differences, e.g. changes in the analysis related to the primary endpoint, a protocol amendment will be considered. The SAP may be updated during the study conduct and will be finalized before final database lock. Any deviations from the planned analysis will be described and justified in the CSR.

The analyses related to the primary and exploratory objectives will be performed when all subjects complete 96 weeks of treatment or until the drug is commercially available in that Country.

Database lock will be associated with the current designated SAP that will describe the analysis up to Week 96 and will be approved and signed prior to the database lock. The analysis results over 96 weeks will be used for the CSR to support publications and marketing activities.

3. STUDY OBJECTIVE AND ENDPOINTS

3.1. Study Objectives

3.1.1. Primary Objective

To evaluate the long-term safety of oral edaravone at a dose of 105 mg administered once daily for 10 days out of a 14-day period, followed by a 14-day drug-free period for 96 weeks of treatment or until the drug is commercially available in that country.

3.1.2. Exploratory Objective

To evaluate the efficacy of oral edaravone at a dose of 105 mg administered once daily for 10 days out of a 14-day period, followed by a 14-day drug-free period, for 96 weeks of treatment or until the drug is commercially available in that country.

3.2. Study Endpoints.

3.2.1. Primary Endpoints

The primary safety endpoints to evaluate the safety and tolerability of oral edaravone will include the following safety assessments:

- Adverse events (AEs), adverse drug reactions (ADRs), and treatment-emergent adverse

Statistical Analysis Plan
Protocol No. MT-1186-A03

Mitsubishi Tanabe Pharma America, Inc.

events (TEAEs);

- Physical examination;
- Body weight;
- 12-lead electrocardiogram (ECG) parameters;
- Vital signs (heart rate, respiratory rate, systolic and diastolic blood pressure, and axillary, oral, or tympanic body temperature [same method is to be used throughout the study]);
- Laboratory safety assessments (e.g. hematology, chemistry, and urinalysis);
- Columbia Suicide Severity Rating Scale (C-SSRS).

3.2.2. Exploratory Endpoint(s)

Exploratory endpoints will include functional and survival assessments of oral edaravone efficacy using the following

- Change in Amyotrophic Lateral Sclerosis Functional Rating Scale-Revised (ALSFRS-R) from baseline to each visit
- Time (days) to death, tracheostomy, or permanent assisted mechanical ventilation (≥ 23 hours/day).

4. STUDY DESIGN

4.1. Study Design

[figure not shown]
This is a Phase 3, international, multi-center, open-label, long-term extension study following the MT-1186-A01 study. The study will evaluate the safety of edaravone at a dose of 105 mg administered once daily for 10 days out of 14, followed by a 14-day drug-free period up to 96 weeks of treatment or until the drug is commercially available in that country.

Subjects who complete treatment in Study MT-1186-A01 and meet eligibility criteria will be enrolled into this open-label treatment study (MT-1186-A03) and will continue to receive 105 mg of edaravone once daily following an overnight fast, and subjects must continue to fast at least 1 to 2 hours before the next meal (e.g., breakfast). Treatment cycles will occur every 28 days (10 days on study drug out of a 14-day period, followed by 14 days off study drug).

Concomitant use of riluzole will be permitted during the study. Subjects who discontinue from the study before Week 96 will complete the procedures listed in Week 96 within 7 days of discontinuation as End of Study (EOS) procedures.

Further details can be found in the Study Schema (Figure 1: Study Schema). The schedules of assessment for each country specific (Germany and France) are referred to each country specific protocol.

Figure 1: Study Schema

Abbreviation: ET = early termination; EOT = end-of-treatment; EOS = end-of-study.

a. Subjects will receive oral edaravone at a dose of 105 mg administered once daily for 10 days out of a 14-day period, followed by a 14-day drug-free period. The dose of edaravone should be taken following an overnight fast and at least 1 to 2 hours before the morning meal.

b. Day 1 is equal to the Week 48 visit of the MT-1186-A01 study.

Table 1: Schedule of Activities for Global

| Assessment | Week (window) | Open-label Treatment Period | | | | | | Safety Follow-up Period ^a |
|--|---------------|---|--------------|--------------|--------------|--------------|------------------------------------|--------------------------------------|
| | | Day 1 (Based upon Week 48 procedures from 1186-A01) | 12 (± 7D) | 24 (± 7D) | 36 (± 7D) | 48 (± 7D) | 60 Telephone Visit (± 7D) | |
| Cycle | 1 | 4 | 7 | 10 | 13 | 16 | 19 | 24 |
| Visit | 1 | 2 | 3 | 4 | 5 | 6 | 7 | 9 |
| Informed consent | X | | | | | | | |
| Eligibility criteria | X | | | | | | | |
| Demographics ^b | X | | | | | | | |
| Vital signs ^c | X | X | X | X | X | X | X | X |
| Orthostatic Vital Sign Assessment | X | X | X | X | X | X | X | X |
| Pregnancy test | X | | | | | X | | X |
| Full Physical examination ^d | X | | | | | | | X |
| Routine physical examination ^d | | X | X | X | X | X | X | |
| 12-lead ECG ^e | X | | | | | X | | X |
| Body weight | X | X | X | X | X | X | X | X |
| Time to event of death, Tracheostomy or permanent assisted mechanical ventilation ^f | X | X | X | X | X | X | X | X |
| Hematology ^g | X | | | X | X | X | X | X |
| Chemistry ^h | X | | | X | X | X | X | X |
| Urinalysis ⁱ | X | | | X | X | X | X | X |

Statistical Analysis Plan
Protocol No. MT-1186-A03

Mitsubishi Tanabe Pharma America, Inc.

| Assessment | Week (window) | Open-label Treatment Period | | | | | | Safety Follow-up Period ^a |
|---|---------------|--|--------------|--------------|--------------|--------------|--------------|--------------------------------------|
| | | Day 1 (Based upon Week 48 procedures from 1186-A01) | 12 (± 7D) | 24 (± 7D) | 36 (± 7D) | 48 (± 7D) | 60 (± 7D) | |
| Cycle Visit | 1 | 4 | 7 | 10 | 13 | 16 | 19 | 24 |
| Dispense edaravone ^b | X | X | X | X | X | X | X | X |
| ALSFRS-R | X | X | X | X | X | X | X | X |
| C-SSRS | X | X | X | X | X | X | X | X |
| Medication Compliance Assessment ^c | | X | X | X | X | X | X | X |
| Adverse events | X | X | X | X | X | X | X | X |
| Concomitant medications | X | X | X | X | X | X | X | X |

Abbreviation: D = Day; ECG = Electrocardiogram; C-SSRS = Columbia-Suicide Severity Rating Scale; ALSFRS-R = Amyotrophic Lateral Sclerosis functional rating scale-revised; EOT = End-of-treatment; ET = early termination.

- Subjects who withdraw from the study will complete the procedures listed in ET within 7 days of study discontinuation. If study treatment is discontinued, study sites must make all efforts to follow-up with phone calls.
- Demographics will include age, sex, race, and ethnicity.
- Vital signs will include systolic and diastolic blood pressure, heart rate, respiratory rate, and axillary, oral or tympanic body temperature (same method is to be used throughout the study).
- Physical examination:
 - A full physical examination will consist of an assessment of major body systems: abdominal, cardiovascular, general appearance, head, eyes, ears/nose/throat, lymph nodes, musculoskeletal, neck, neurological, dermatological, respiratory, and other.
 - Routine physical examination will include abdominal, cardiovascular, general appearance, respiratory, neurological, and other.
- A 12-lead ECG will be performed after the subject has rested for at least 5 minutes in a supine position. The ECG must include the following measurements: R wave to R wave (RR) interval, heart rate, QRS, QT, QTcB, and QTcF. The Investigator will perform an overall evaluation of the ECG for safety purposes and the recording will be reported as 'normal', 'abnormal clinically significant (CS)', or 'abnormal not clinically significant (NCS)'. Abnormalities of clinical significance will be reported as AEs.
- Events are time to death, tracheostomy, or permanent assisted mechanical ventilation (> 23 hours/day).
- To include: Red blood cell count, hemoglobin, hematocrit value, white blood cell count including differential, and platelet count

Statistical Analysis Plan
Protocol No. MT-1186-A03

Mitsubishi Tanabe Pharma America, Inc.

- h. To include: albumin, total protein, aspartate aminotransferase (AST), alanine aminotransferase (ALT), lactate dehydrogenase (LDH), alkaline phosphatase (ALP), total bilirubin, direct bilirubin, CK, total cholesterol, triglycerides, BUN, bicarbonate, serum glucose, serum creatinine level, uric acid, sodium (Na), potassium (K), chloride, and calcium (Ca). Note: albumin will be included in the chemistry profile for Weeks 24, 48, 72 and 96 only. The Day 1 screening assessment will not include albumin as it was not collected as part of Study MT-1186-A01 chemistry profile.
 - i. To include protein, glucose, occult blood, urobilinogen, white blood cells, and bilirubin.
 - j. Subjects will receive oral edaravone at a dose of 105 mg administered once daily for 10 days out of a 14-day period, followed by a 14-day drug-free period for 96 weeks of treatment or until the drug is commercially available in that country. The dose of edaravone should be taken following an overnight fast and at least 1 to 2 hours before the morning meal.
 - k. Drug compliance should be assessed on a per cycle basis by site staff via phone calls or during the in-clinic visits.

| Assessment | Open-label Treatment Period | | | | | | Safety Follow-up Period* |
|--|---|-------------------|-------------------|-------------------|-------------------|-------------------|--------------------------|
| | Day 1 (Based upon Week 48 procedures from 1186-A01) | 12 (\pm 7D) | 24 (\pm 7D) | 36 (\pm 7D) | 48 (\pm 7D) | 60 (\pm 7D) | |
| Cycle | 1 | 4 | 7 | 10 | 13 | 16 | 24 |
| Visit | 1 | 2 | 3 | 4 | 5 | 6 | 7 |
| Informed consent | X | | | | | | |
| Eligibility criteria | X | | | | | | |
| Demographics ^b | X | | | | | | |
| Vital signs ^c | X | X | X | X | X | X | X |
| Orthostatic Vital Sign Assessment | X | X | X | X | X | X | X |
| Pregnancy test | X | | | | X | | X |
| Full Physical examination ^d | X | | | | | | |
| Routine physical examination ^d | | X | X | X | X | X | |
| 12-lead ECG ^e | X | | | | X | | X |
| Body weight | X | X | X | X | X | X | X |
| Time to event of death, Tracheostomy or permanent assisted mechanical ventilation ^f | X | X | X | X | X | X | X |
| Hematology ^g | X | | X | X | X | X | X |
| Chemistry ^h | X | | X | X | X | X | X |

Statistical Analysis Plan
Protocol No. MT-1186-A03

Mitsubishi Tanabe Pharma America, Inc.

Assessment

| Assessment | Open-label Treatment Period | | | | | | | Safety Follow-up Period* |
|---|-----------------------------|--|-------------------|-------------------|---|-------------------|---|--------------------------|
| | Week (window) | Day 1 (Based upon Week 48 procedures from 1186-A01) | 12 (\pm 7D) | 24 (\pm 7D) | 36 Telephone Visit or In-Clinic Visit (\pm 7D) | 48 (\pm 7D) | 60 Telephone Visit or In-Clinic Visit (\pm 7D) | |
| Cycle | 1 | 4 | 7 | 10 | 13 | 16 | 19 | 24 |
| Visit | 1 | 2 | 3 | 4 | 5 | 6 | 7 | 8 |
| Urinalysis [†] | X | | X | | X | | X | X |
| Dispense edaravone [‡] | X | | X | | X | | X | |
| ALSFRS-R | X | | X | | X | | X | X |
| C-SSRS | X | | X | | X | | X | X |
| Medication Compliance Assessment [§] | | X | X | X | X | X | X | X |
| Adverse events | X | X | X | X | X | X | X | X |
| Concomitant medications | X | X | X | X | X | X | X | X |

Abbreviation: D = Day; ECG = Electrocardiogram; C-SSRS = Columbia-Suicide Severity Rating Scale; ALSFRS-R = Amyotrophic Lateral Sclerosis functional rating scale- revised; EOT = End-of-treatment; ET = early termination.

- Subjects who withdraw from the study will complete the procedures listed in ET within 7 days of study discontinuation. If study treatment is discontinued, study sites must make all efforts to follow-up with phone calls.
- Demographics will include age, sex, race, and ethnicity.
- Vital signs will include systolic and diastolic blood pressure, heart rate, respiratory rate, and axillary, oral or tympanic body temperature (same method is to be used throughout the study).
- Physical examination.

- A full physical examination will consist of an assessment of major body parts and systems: abdominal, cardiovascular, general appearance, head, eyes, ears/nose/throat, lymph nodes, musculoskeletal, neck, neurological, dermatological, respiratory, and other.
- Routine physical examination will include abdominal, cardiovascular, general appearance, respiratory, neurological, and other.
- A 12-lead ECG will be performed after the subject has rested for at least 5 minutes in a supine position. The ECG must include the following measurements: R wave to R wave (RR) interval, heart rate, QRS, QT, QTcB, and QTcF. The Investigator will perform an overall evaluation of the ECG for safety purposes and the recording will be reported as 'normal', 'abnormal clinically significant (CS)', or 'abnormal not clinically significant (NCS)'. Abnormalities of clinical significance will be reported as AEs.

Statistical Analysis Plan
Protocol No. MT-1186-A03

Mitsubishi Tanabe Pharma America, Inc.

- f. Events are time to death, tracheostomy, or permanent assisted mechanical ventilation (> 23 hours/day).
- g. To include: Red blood cell count, hemoglobin, hematocrit value, white blood cell count including differential, and platelet count
- h. To include: albumin, total protein, aspartate aminotransferase (AST), alanine aminotransferase (ALT), lactate dehydrogenase (LDH), alkaline phosphatase (ALP), total bilirubin, direct bilirubin, gamma-glutamyl transferase (GGT), CK, total cholesterol, triglycerides, BUN, bicarbonate, serum glucose, serum creatinine level, uric acid, sodium (Na), potassium (K), chloride, and calcium (Ca). Note: albumin will be included in the chemistry profile for Weeks 24, 48, 72 and 96 only. The Day 1 screening assessment will not include albumin as it was not collected as part of Study MT-1186-A01 chemistry profile.
- i. To include protein, glucose, occult blood, urobilinogen, white blood cells, and bilirubin.
- j. Subjects will receive oral edaravone at a dose of 105 mg administered once daily for 10 days out of a 14-day period, followed by a 14-day drug-free period for 96 weeks of treatment or until the drug is commercially available in that country. The dose of edaravone should be taken following an overnight fast and at least 1 to 2 hours before the morning meal.
- k. Drug compliance should be assessed on a per cycle basis by site staff via phone calls or during the in-clinic visits.

4.2. Sample Size and Power Considerations

The study sample size is not based on power and statistical considerations. This study serves as an extension to MT-1186-A01 (the Parent study) and, as such, will roll over subject to the current study. The total number of subjects enrolled will depend on the number of subjects who complete the MT-1186-A01 study and are also eligible and consent to participate in this extension study. Approximately 140 patients will potentially be enrolled in Study MT-1186-A03.

5. PLANNED ANALYSIS

5.1. Interim Analysis

No Interim Analysis is planned for this Study.

5.2. Final Analysis

Final analyses related to the primary and exploratory objectives will be performed when all subjects complete week 96 or until the drug is commercially available in that country.

5.3. Data Monitoring Committee

Not Applicable

6. ANALYSIS POPULATIONS

6.1. Safety Analysis Population

The safety analysis population set is defined as all enrolled subjects to A03 who received at least 1 dose of oral edaravone.

6.2. Full Analysis Set:

The Full Analysis (FAS) is defined as all patients in the MT-1186-A01 SAF as defined in protocol MT-1186-A01. This analysis set will include patients who discontinued treatment during MT-1186-A01.

7. STATISTICAL CONSIDERATIONS

7.1. Descriptive Statistics

All data from all subjects enrolled into the study will be included in patient data listings. The listings will be sorted by center and subject number (and by visit, if applicable).

Continuous data will be summarized descriptively using the number in the analysis population set (N), the number of observations (n), mean, standard deviation (SD), median, minimum and maximum. Categorical data will be summarized using frequency counts and percentages. The denominator for the percentages will be the total number of subjects in the treatment group and analysis population being presented, unless otherwise specified. For visit-specific data, the number of subjects with non-missing observations at the visit in question will be used as the denominator for percent calculations. Unknown, Not Done, Not Applicable and other classifications of missing data will not be considered.

7.2. Statistical Tests

This study is a long-term, open-label safety study. As a result, no formal hypothesis testing is planned for this study. The long-term safety and tolerability of oral edaravone will be evaluated in exploratory manner using descriptive statistics. For exploratory efficacy analysis, point estimates and their associated 95% Confidence Interval will be presented.

8. DATA CONVENTIONS

8.1. Baseline Definition

In general, the data at Week 48 in Study MT-1186-A01 (same time as A03 Visit 1/Day 1) will be used as the baseline for statistical analysis in this study. The analyses involving calculation of change from baseline will be based on the absolute changes from baseline (not percentage), unless stated otherwise.

The time (days) to death, tracheostomy, or permanent assisted mechanical ventilation (≥ 23 hours/day) will be analyzed using the time from first study drug administration in the MT-1186-A01 study.

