### **8.2.2 Rational for Dose Selection**

Findings from Study MT-1186-J03 demonstrated that a 105 mg oral suspension dose of edaravone has an equivalent AUC to the approved 60 mg/60 min IV dose (geometric mean ratio [90% CI]: 0.977 [0.917, 1.041]). The geometric mean ratio of the  $C_{max}$  of the 105 mg oral suspension compared to the 60 mg/60 min IV infusion was also within bioequivalence range, but the upper limit of 90% CI exceeded 1.25 (geometric mean ratio [90% CI]: 1.217 [1.090, 1.359]). This was the dose given in the MT-1186-A01 study, and therefore, the 105 mg dose has been selected for this study as well.

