### **9.3 Inclusion Criteria**

Subjects who meet all the following criteria will be considered eligible to participate in the study:

1. Subjects must provide signed and dated informed consent form (ICF) to participate in the study.
2. Subjects must be able to (in the judgment of the Investigator) understand the nature of the study and all risks involved with participation in the study.
3. Subjects must be willing to cooperate and comply with all protocol restrictions and requirements
4. Subjects who successfully completed all Study MT-1186-A01 visits and have been compliant with study drug.

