### **17.3.2 Data Handling**

#### **17.3.2.1 Definition of Baseline for the Efficacy and Safety Endpoints**

The data at Week 48 in Study MT-1186-A01 will be used as the baseline for statistical analysis in this study. The time (days) to death, tracheostomy, or permanent assisted mechanical ventilation ( $\geq 23$  hours/day) will be analyzed using the time from the first study drug administration in the MT-1186-A01 study.

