### **17.3.5 Efficacy Analysis**

#### **17.3.5.1 ALSFRS-R Scores**

The ALSFRS-R scores will be assessed on the SAF analysis set and will present change from baseline to each visit using descriptive statistics and 95% CI at each visit.

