9.3.3. Laboratory Tests

All laboratory data will be listed and only central laboratory data will be analyzed. Laboratory data and change from baseline (haematology, biochemistry or urinalysis) will be summarized with descriptive statistics (continuous variables) or as distributions (categorical variables) by visit up to week 96 except for pregnancy test parameter. For urinalysis parameter, a shift table from baseline up to Week 96 will be presented.

The categories for out of reference range will be Low, Normal and High for Hematology, Biochemistry and Urinalysis, and Normal and Abnormal for Urinalysis (Qualitative Value). For these categories, a shift table from baseline to each visit up to Week 96 will be presented.

Laboratory test values will be considered potentially clinical significant (PCS) if they meet either the low or high PCSV criteria listed in section 8.4.3.3. A shift table describing the number and percentage of subjects shifting from non PCSV at baseline to PCSV at post-baseline will be performed any time during treatment period.

The percentages will be calculated from the number of subjects with available baseline values and any time post-baseline value

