10.2. Treatments to Report

| Treatment | For TFLs |
|--|---------------------------------|
| MT-1186 105 mg oral suspension, administered for 10 days out of 14-day period, followed by a 14-day drug-free period for Cycles 1-24 for a total of 96 weeks | MT-1186 105 mg (2 Weeks On/Off) |

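### Baseline is A01 Week 48, on treatment, so a change that arose in A01 and persisted cannot appear as a change from baseline or as a PCSV shift

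*SAP*

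**What the plan says.** Both documents set the same baseline. SAP 8.1 says that "the data at Week 48 in Study MT-1186-A01 (same time as A03 Visit 1/Day 1) will be used as the baseline for statistical analysis", and Protocol 17.3.2.1 says: "The data at Week 48 in Study MT-1186-A01 will be used as the baseline for statistical analysis in this study".

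This is an on-treatment value. Protocol 8.2.2 says of 105 mg: "This was the dose given in the MT-1186-A01 study, and therefore, the 105 mg dose has been selected for this study as well". Protocol 9.3 limits entry to "Subjects who successfully completed all Study MT-1186-A01 visits and have been compliant with study drug". A03 then adds 24 more cycles; SAP 10.2 describes the regimen as dosing "followed by a 14-day drug-free period for Cycles 1-24 for a total of 96 weeks".

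SAP 8.4.3 restricts safety outcomes to those observed in A03 unless otherwise specified. SAP 9.3.3 to 9.3.5 summarise values and changes from baseline by visit for laboratory tests, vital signs with weight, and ECG. For the PCSV criteria, SAP 9.3.3 plans this: "A shift table describing the number and percentage of subjects shifting from non PCSV at baseline to PCSV at post-baseline". The denominator rule follows: "The percentages will be calculated from the number of subjects with available baseline values and any time post-baseline value". In SAP 8.4.3.3 every PCSV criterion is a level or a multiple of the upper limit of normal, except hematocrit, which also needs a fall of at least 3 percentage points from baseline.

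The time-to-event endpoint has a different origin. It runs from the first A01 dose in the FAS, that is, the A01 safety set (SAP 6.2, 8.1, 9.2.1.2).

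**The concern.** The primary objective is long-term safety, and the subjects' exposure at this dose starts in A01. With the reference at Week 48, three things follow for a change that developed in A01 and stayed.

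- It is part of the baseline, so the change-from-baseline tables show only what was added afterwards.
- A subject already PCSV at Week 48 cannot be counted in the shift table on that criterion, however far the value moves later. As worded, that subject still counts in the denominator.
- For hematocrit, a fall that began in A01 may be too small when measured from Week 48 to meet the criterion.

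At stake is whether the report can show how far a subject has moved since starting A01 treatment. With no control arm, within-subject change is one of the few comparisons available.

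**Working it through.** The plan gives no power, rate or effect figure to reproduce: about 140 subjects is a roll-over count (SAP 4.2), and no hypothesis test is planned (SAP 7.2). The figures below illustrate what the rules do, and their inputs are assumed where marked.

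**1. Share of a cumulative change left in view.** Nominal treatment span: 48 + 96 = 144 weeks, of which 48/144 = 33.3% lies before the baseline.

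- Linear drift (assumed): share seen from Week 48 = 96/144 = 66.7%.
- Change that levels off (assumed half-life H, k = ln 2 / H): share = [exp(−48k) − exp(−144k)] / [1 − exp(−144k)].
  - H = 48 weeks: (0.5 − 0.125)/0.875 = 42.9%
  - H = 24 weeks: 23.8%
  - H = 12 weeks: 6.2%
  - H = 4 weeks: about 0%

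Measured from the start of A01, the share is 100% in each case.

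**2. PCSV shift count and denominator.** Assumed: 140 subjects, constant hazard, abnormality persists once reached, no dropout. If a proportion p becomes PCSV over 144 weeks, the number already PCSV at Week 48 is 140 × [1 − (1 − p)^(1/3)].

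For p = 20%: total 140 × 0.20 = 28; already PCSV 140 × (1 − 0.8^(1/3)) = 10.0; counted as shifts 28 − 10.0 = 18.0. As worded, the percentage is 18.0/140 = 12.8%. Among those who can shift, it is 18.0/(140 − 10.0) = 13.8%.

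| p over 144 weeks | Total PCSV | Already PCSV at Week 48 | Counted as shift | % of 140 | % of those non-PCSV at baseline |
|---|---|---|---|---|---|
| 5% | 7 | 2.4 | 4.6 | 3.3 | 3.4 |
| 10% | 14 | 4.8 | 9.2 | 6.5 | 6.8 |
| 20% | 28 | 10.0 | 18.0 | 12.8 | 13.8 |
| 30% | 42 | 15.7 | 26.3 | 18.8 | 21.2 |

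The denominator effect is the gap between the last two columns. The uncounted subjects are the larger effect: about a third of the total under these assumptions.

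**3. Two invented subjects, applied to SAP 8.4.3.3.**

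- Male, hematocrit 45% before A01, 38% at Week 48, 36% in A03. The level condition (37% or below) is met. The fall from the A03 baseline is 38 − 36 = 2 points, short of 3, so he is not PCSV. From the pre-A01 value it is 45 − 36 = 9 points.
- Male, hemoglobin 11.4 g/dL at Week 48. The limit is 11.5 g/dL or below, so he is already PCSV and no later value can make him a shift.

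**4. Outputs that do not depend on change.** SAP 9.3.3 also plans laboratory values by visit, Low/Normal/High shift tables to each visit, and a listing of all laboratory data. SAP 9.3.4 and 9.3.5 add vital signs and weight by visit, orthostatic hypotension by visit (defined within the visit in SAP 8.4.3.5) and the investigator's ECG category by visit. SAP 10.3 includes the Baseline visit. The hemoglobin subject above would therefore appear in the by-visit values and, if below the reference range, in the Low-to-Low cell. He is missing only from the PCSV shift count.

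**The case against.** The strongest defence is that the baseline fits the stated objective. The objective is safety over 96 weeks of A03 treatment, both documents agree on the reference, and the analysis is descriptive. A01 has its own protocol, and its report may cover the first 48 weeks. This stands in part: there is no inconsistency or arithmetic error, and what A01 reports cannot be judged from these documents. It does not remove the gap for a change that spans both studies, which the A03 tables as planned would not show as one change.

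A reader might infer that changes from the first year disappear from the long-term safety tables altogether. Step 4 shows that they do not: a persistent abnormality stays visible as a level or a category. Adverse event reporting helps less, because SAP 9.3.1 leaves out events that occurred in A01. That loss comes from the adverse event rules, not from SAP 8.1.

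A reader might also infer that A01 data enter the analysis only through the time-to-event endpoint. In fact the SAP uses them for disposition (9.1.1), baseline characteristics and ALS history (8.4.1.2) and the Oral/PEG classification (8.4.3.1).

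Nor can the pre-A01 value be called untreated: SAP Table 4 records edaravone exposure before A01.

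Finally, Protocol 17.3.5.1 says: "The ALSFRS-R scores will be assessed on the SAF analysis set and will present change from baseline to each visit". It is tempting to put a size on how much slower the roll-over subjects decline. The documents give no slope, spread or exit rate, so any size would rest on an assumed link between decline and exit. It would also measure selection into A03, not the choice of baseline.

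**Conclusion.** The point holds as a limit on interpretation. Change-from-baseline and PCSV-shift results cannot show a change that arose in A01 and persisted, although the abnormality itself remains visible elsewhere. Under the assumed patterns, between about 0% (early plateau) and 66.7% (linear drift) of the 144-week change stays in view as change.

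The denominator fault is real but minor: 12.8% against 13.8% in the 20% scenario, assuming constant hazard, persistence and no dropout. The hematocrit problem is confined to that criterion, the only one with a change component. Albumin is unaffected, since SAP 8.4.3.3 already rules out change from baseline for it.

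The documents do not support going further, to hidden abnormalities or to a stated bias in the ALSFRS-R decline.

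**What to change.** Keep the planned A03-baseline tables and make two changes to the SAP.

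1. **Section 9.3.3.** Calculate the PCSV shift percentage among subjects who are non-PCSV at baseline and have a post-baseline value. Show those already PCSV at A03 baseline in a separate row. For hematocrit that row will be empty by construction, because no one has fallen from baseline at baseline; only the second change helps there.
2. **Sections 8.1 and 9.3.3 to 9.3.5.** Define a supplementary baseline as the last value before the first A01 dose. Against it, add change tables for laboratory values, weight, vital signs and ECG, and a PCSV table that includes the hematocrit criterion. Limit this to parameters that A01 collected, so not albumin, and show results by edaravone exposure before A01.

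A 144-week ALSFRS-R analysis on the FAS is optional and exploratory. The documents do not say whether ALSFRS-R was collected after subjects left A01, so it may not match the follow-up behind the survival analysis.

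The cost is a few more tables, run on data from a study that the SAP already draws on, with no new data collection. Some rates may look less favourable.
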